Research Proposal

Research title:

Effects of Expressive Writing on Stress and Work-Related Outcomes among Student Nurse Interns: a randomized controlled trial

NCT ID:

Not yet assigned

Date of the document:

[figure not shown]
October 17th, 2023

Research title:

Effects of Expressive Writing on Stress and Work-Related Outcomes among Student Nurse Interns: a randomized controlled trial

Funding sources:

Supported by the Program for the Philosophy and Social Sciences Research (PSSR) of Higher Learning Institutions of Shanxi, China (Project No.: 2023W103)

Research schedule:**Ethical Review:**

The Ethics Committee of Changzhi Medical College approved the study protocol on October 17, 2013, registration number RT2023047.

1. Introduction

Nursing internships are essential to nursing programs and a crucial stage in the early careers of nursing students. Those seeking hands-on experience in hospitals or medical facilities are known as student nurse interns. The clinical learning experience is considered a significant source of stress. The

stress level of nursing students during clinical practicum ranges from moderate to severe, affecting 47.82 to 100% of participants.

Stressors in the clinical setting included discrepancy between theory and practice, feeling unprepared, fear of making a mistake, issues related to death and dying, witnessing suffering, challenging interpersonal relationships with clinical staff, being observed and evaluated, communication with physicians, conflict between personal life and internship tasks, and unfamiliarity with the hospital environment. The rapid evolution of healthcare brings new stressors for nurses and nursing students. Health professionals often play down or deny mental health problems, which exacerbates the problem.

Stress not only affects the well-being of student nurse interns but also impacts job satisfaction and can lead to turnover in nursing. The stress of student nurse interns can affect motivation, communication, learning, clinical practice, and academic performance, which can be detrimental to patients. The American College Health Association (ACHA) and the Chinese Ministry of Education have taken steps to promote student mental health. Academic institutions actively conduct mental health research to develop effective strategies and programs.

Stress management interventions (SMI), non-pharmacological approaches to managing psychological and physical stress, show promise in reducing stress among nursing students. Although SMIs have demonstrated efficacy, more studies on senior students and Chinese student nurse interns are needed.

According to the transactional model of stress and coping proposed by Lazarus and Folkman, the three targets of effective stress management are stressors, coping strategies, and cognitive reappraisal. The stressor refers to any event or internal or external environmental stimulus that can be perceived

by an individual and elicit a positive or negative stress response; the coping strategy refers to the process by which an individual deals with internal or external demands that are perceived as stressful or exceed the resources of the individual; cognitive reappraisal is the method of changing an individual's evaluation of the stressor and self-defeating perception of stress.

Expressive writing (EW) is a form of writing therapy (WT) introduced by James Pennebaker in 1986. It enables individuals to express important emotional events they have experienced, to write down their deepest feelings and thoughts, and to find positive meaning in advert events. Following the transactional model of stress and coping, EW encompasses all three targets of stress reduction (using stressors as a writing topic, writing as a form of coping, and cognitive reappraisal during the writing process). At the same time, its simplicity, cost-effectiveness, brevity, and low expertise requirements make EW an easily accessible intervention method.

As there are few studies on the effectiveness of EW with student nurse interns, this study aims to investigate the efficacy of expressive writing in managing stress and work-related outcomes in student nurse interns, which may provide a valuable new approach.

2. Research Questions

- Is there any difference between the four repeated (at immediate, 4-week, 8-week, and 12-week follow-up) clinical practice stress tests between the intervention and control group in terms of the mean?
- Is there any difference between the four repeated (at immediate, 4-week, 8-week, and 12-week follow-up) coping strategy tests between the intervention and control group in terms of the mean of positive coping and negative coping?

- Is there any difference between the four repeated (at immediate, 4-week, 8-week, and 12-week follow-up) work engagement tests between the intervention and control group in terms of the mean?
- Is there any difference between the four repeated (at immediate, 4-week, 8-week, and 12-week follow-up) perceived professional benefit tests between the intervention and control group in terms of the mean?

3. Research Objectives

General objective:

Evaluate the impact of expressive writing (EW) intervention on stress and work-related outcomes among Chinese student nursing interns

Specific objectives:

- To compare the effectiveness of EW (expressive writing) and NW (neutral writing) in managing clinical practice stress among student nurse interns between intervention and control groups at immediate and 4-week, 8-week, and 12-week follow-up.
- To compare the impact of EW and NW on improving coping strategies among student nurse interns between intervention and control groups at immediate and 4-week, 8-week, and 12-week follow-up.
- To evaluate the effectiveness of EW and NW in promoting work engagement between intervention and control groups at immediate and 4-week, 8-week, 12-week follow-up.
- To compare the impact of EW and NW on promoting perceived professional benefit among student nurse interns between intervention and control groups among student nurse interns at immediate and 4-week, 8-week, and 12-week follow-up.

4. Study Design

A randomized controlled trial with parallel design.

5. Inclusion and Exclusion Criteria of Participants

Inclusion criteria:

- Undergraduate student nurse interns in their first clinical internship (had no prior clinical practice experience)
- Have access and proficiency in utilizing social media
- Be able to read and write via the internet
- Be willing to fill in questionnaires and write according to the assigned writing prompts
- Never participated in an expressive writing or stress management intervention programs

Exclusion criteria:

- Intern at a self-contacted hospital
- Severe current psychological conditions
- Undergoing any form of psychotherapy
- With a habit of keeping diaries

Withdrawal criteria:

- Termination of internship for whatever reason
- Not submitting writing materials twice

6. Sample Size

Using the sample size formula for comparing the means of two independent samples of continuous variables to calculate the sample size.

$$n_i = 2 \left(\frac{Z_{1-\alpha/2} + Z_{1-\beta}}{ES} \right)^2$$

$$ES = \frac{|\mu_1 - \mu_2|}{\sigma}$$

To detect between-group differences with an effect size of 0.69 in clinical practice stress by Stress Rating Scale for Nursing Students in Practice after 10 weeks of intervention (primary outcome), with an α level of 0.05, we require 33 participants per group to attain a power of 80%. Accounting for an expected 10% loss to follow-up, we should include 74 participants.

7. Sampling and Grouping

All eligible student nurse interns in the four target hospitals constituted the sampling frame. Two of the four target hospitals will be selected by lottery and the intervention and control groups will be determined by a coin toss.

Participants will be sampled for both the intervention and control groups using the following method: all potential participants were entered alphabetically into Column A of the Excel sheet from A to Z. Then, random numbers will be generated in column B of the Excel sheet using the Rand() function. The 37 participants with small random numbers will be included as study participants in both groups.

A research assistant who will not be involved in other parts of the study completed all the above processes.

8. Blinding

This is a single-blinded randomized controlled study.

The intervention trainer will not be blinded, given that a single researcher conducts the study. To minimize experimenter bias, outcome assessments will be conducted through an online questionnaire survey platform (Wenjuanxing), with the trainer distributing the same link to all participants. During data

collection, only acronyms of the questionnaires will be used to avoid self-fulfilling expectations.

Participants will be informed during the recruitment phase only that the study aimed to explore the effect of writing on internship experience and feelings. Assignment to the intervention or control group will remain undisclosed to participants until the end of the 3-month follow-up.

Participants could unblind themselves by exiting the study and requesting debrief information.

9. Intervention Description

Intervention group:

According to the writing prompts, online expressive writing focuses on stressful events and will be conducted twice a week (every Monday and Thursday) for 15 minutes each time, lasting for ten weeks.

Writing prompts are developed based on Emotional Processing Theory (EPT) and Cognitive Adaptation Theory (CAT).

- 1st writing/Monday:

[figure not shown]
Describe the distressing/stressful event (like workload, lack of break/leisure time, knowledge proficiency, patient care, interpersonal communication, role adaptation...) with causal links between the event's segments; describe your thoughts and feelings at the time of the event; describe what you did to keep the event under control.

In your writing, I'd like you to let go and explore your deepest emotions and thoughts. You might tie your topic to your relationships with others, including parents, lovers, friends, or relatives; to your past, your present, or your future; or to who you have been, who you would like to be or who you are now. Don't worry about spelling, grammar, or sentence structure. The only rule is that once you begin writing, you continue until the time is up.

- 2nd writing/Thursday:

Reflect on how the event you wrote about in your first writing of this week affected your life (any gains or growth); how you currently think and feel about the event; whether or not you are grateful it did not get worse; where do you

Cognitive Adaptation Theory (CAT)

Emotional processing theory (EPT)

feel you did well in this coping; future coping with a similar event.

In your writing, I'd like you to let go and explore your deepest emotions and thoughts. You might tie your topic to your relationships with others, including parents, lovers, friends, or relatives; to your past, your present, or your future; or to who you have been, who you would like to be or who you are now. Don't worry about spelling, grammar, or sentence structure. The only rule is that once you begin writing, you continue until the time is up.

Control group:

According to the writing prompts, online neutral writing focuses on immediate surroundings and will be conducted twice a week (every Monday and Thursday) for 15 minutes each time, lasting for ten weeks. Writing prompts are as follows:

- 1st writing/Monday:

Describe the specified object (from week one to week ten, specify the specified object as "the door you see now", "your hairstyle", "the pants you are wearing", "the room you are in", "your hands", "the shoes you are wearing", "the view from the window", "the clothes you are wearing", "your water bottle" and "your phone/computer").

In your writing, concentrate on the facts and details of the activity and thing you chose. We are not interested in your emotions or opinions, rather we want you to try to be completely objective. Feel free to be as detailed as possible.

- 2nd writing/Thursday:

Describe the specified object in the picture (from week one to week ten, provide pictures of the door, hairstyle, pants, room, hands, shoes, view from a window, clothes, water bottle, and computer).

In your writing, concentrate on the facts and details of the activity and thing you chose. We are not interested in your emotions or opinions, rather we want you to try to be completely objective. Feel free to be as detailed as possible.

To ensure the effectiveness of online writing, we developed a webpage suitable for the program. Participants can write from their computers or mobile devices. When a participant goes to the web page, the first page will be the instructions. This page shown before the writing tasks described the main objective of each task, emphasizing the importance of carefully reading the instructions. After reading the instructions, participants fill in their unique number and click on the "start writing" button. Then it will turn to the second

page for writing. There will be a countdown clock on this page, with the remaining time for the task. The clock flashed when one minute remained. When the time expires, the writing page will automatically close and display the final text. At this point, no editing was possible, but participants could read their texts.

10. Outcome Measures

All measures will be taken one day before the start of the intervention, one day after the end of the intervention, and followed up at 4 weeks, 8 weeks, and 12 weeks after the end of the intervention.

Primary outcome: Clinical Practice Stress

Stress Rating Scale for Nursing Students in Practice

The scale consists of 6 dimensions and 37 entries, including the nature of work, workload, preparation for an internship, interpersonal relationships, work support, and learning and work impulse. The scale rates on a 4-point Likert scale, with no stress, mild stress, moderate stress, and severe stress, assigned a score of 0, 1, 2, and 3, respectively, and the higher the score, the greater the stress.

Secondary outcome: Coping Strategy, Work Engagement, Perceived Professional Benefit

Brief Coping Style Scale

The scale consists of two dimensions, positive and negative coping, with 20 entries. A 4-point Likert scale is used, with 1-4 indicating "not used" to "often used". Positive coping has 12 entries, and negative coping has 8 entries, with higher scores indicating more frequent use of coping strategies.

Utrecht Work Engagement Scale

The scale consists of 3 dimensions: vitality, dedication, and concentration, comprising 15 entries. A 7-point Likert scale is used, with scores ranging from 0-6 for "never," "almost never," "rarely," "sometimes," "often," "frequently," and "always." The total score is the sum of the scores of each entry. An average entry score of 4 or more is defined as a high level of work engagement, 2-4 as a moderate level, and less than 2 as a low level of work engagement.

Perceived Professional Benefits Scale

The scale consists of 7 items of positive career sense, 6 items of good nurse-patient relationship, 6 items of sense of belonging to the team, 8 items of self-growth, and 6 items of identification with friends and relatives, 33 items in 5 dimensions in total, and each item is scored 1 to 5 on a 5-point Likert scale ranging from "strongly disagree" to "strongly agree. The higher the score, the stronger the perceived professional benefit.

11. Data Analysis

Data will be analyzed with Stata version 14. All endpoints will be analyzed with generalized estimating equations and will use robust standard errors. The working correlation structure will be specified as exchangeable.

Data from all available time points will be used. The independent variables included in the model will be the treatment group (categorical) and the baseline value of the dependent variable (continuous). A model that additionally adjusted for age and sex for the primary endpoint will run.

The primary endpoint and secondary endpoints will all be analyzed with an intention-to-treat approach.

References

Ahmad, T. B., & Meltem Meriç, R. (2021). The effect of an online psychoeducational stress management program on international students'

ability to cope and adapt. *Perspectives in Psychiatric Care*, 57(4), 1673-1684. doi:10.1111/ppc.12735

Aloufi, M. A., Jarden, R. J., Gerdtz, M. F., & Kapp, S. (2021). Reducing stress, anxiety, and depression in undergraduate nursing students: Systematic review. *Nurse Education Today*, 102, 104877. doi:10.1016/j.nedt.2021.104877

Aslan, H., & Pekince, H. (2021). Nursing students' views on the COVID-19 pandemic and their perceived stress levels. *Perspectives in Psychiatric Care*, 57(2), 695-701. doi:10.1111/ppc.12597

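### Two missed submissions lead to withdrawal before any outcome is measured, and the protocol does not say that withdrawn interns are still followed for the intention-to-treat analysis

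*Protocol*

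**What the plan says.** - **Protocol, Section 5, Withdrawal criteria:** an intern is withdrawn for "Not submitting writing materials twice". It is not stated whether the two misses are counted cumulatively or must be consecutive, or what withdrawal means for later questionnaires.
- **Section 5, Inclusion criteria:** interns must "Be willing to fill in questionnaires and write according to the assigned writing prompts", which is agreement to two separate things.
- **Section 8:** the only other text on leaving is "Participants could unblind themselves by exiting the study and requesting debrief information". It concerns interns who choose to go and mentions no further measurement. The questionnaires go out "with the trainer distributing the same link to all participants", which is offered as protection against experimenter bias.
- **Section 9:** expressive writing is "conducted twice a week (every Monday and Thursday) for 15 minutes each time, lasting for ten weeks". The neutral-writing control follows the same timetable.
- **Section 10:** measurements are taken "one day before the start of the intervention, one day after the end of the intervention", and participants are then "followed up at 4 weeks, 8 weeks, and 12 weeks after the end of the intervention". Nothing is measured during the writing weeks.
- **Section 11:** all endpoints are analysed by intention to treat, in a GEE with treatment group and the baseline value of the outcome as independent variables, using whatever time points are available.

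**The concern.** Section 5 can remove an intern for behaviour that occurs after allocation. Intention to treat requires that such behaviour does not decide who is analysed. The two sections are compatible only if withdrawn interns are still measured, and the protocol does not say that they are. Leaving the study is the ordinary meaning of a withdrawal criterion, and staff who follow it that way would stop sending questionnaires.

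The arms have different tasks: one writes about stressful events, the other describes neutral objects. Who misses sessions could therefore differ by arm and could be related to stress, the primary outcome. The document does not show that this happens. If it did, the interns who remain would no longer represent the groups as allocated, although the analysis would still be called intention-to-treat. Questionnaires that were never sent cannot be recovered later, so the matter has to be settled before data collection.

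**Working it through.** **The plan's own figure.** Section 6 uses effect size 0.69, two-sided α 0.05 and power 80%: n = 2 × ((1.960 + 0.842)/0.69)² = 32.97, so 33 per group. Allowing 10% loss, 33/0.9 = 36.7, so 37 per group and 74 in total. Both figures reproduce, and this point does not change them.

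**When the rule can act.** Take Monday of week 1 as day 1.

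- Sessions per arm: 2 × 10 = 20.
- Earliest second miss, on either reading: session 2, Thursday of week 1, day 4.
- Latest second miss, on either reading: session 20, Thursday of week 10, day 67 (9 × 7 + 4).
- First post-baseline measurement: day 68 if the intervention ends with session 20, or day 71 if it ends with week 10.
- Gap from second miss to first measurement: 68 − 4 = 64 days down to 68 − 67 = 1 day, or 71 − 4 = 67 days down to 71 − 67 = 4 days.

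Every possible trigger precedes the first outcome measurement.

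**What is lost if measurement stops.** There are 5 scores (stress, positive coping, negative coping, work engagement, professional benefit) at 4 post-baseline times, so 20 of 20 records are lost. Baseline is a covariate in the GEE and not an outcome row. The intern therefore has no row in any model, and using all available time points does not help because none is available.

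**How strict the rule is.**

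- Cumulative: at most 1 miss, so at least 19 of 20 submissions (95%).
- Consecutive: no two adjacent misses in 20 sessions allows at most 10 misses, so at least 10 of 20 submissions (50%).

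The retained set is selected on adherence under both readings, but consists of near-complete adherers only under the first.

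**Illustration of numbers withdrawn.** The per-session miss rate m is an assumption, as the protocol gives none, and sessions are taken as independent. On the cumulative reading the share withdrawn is 1 − (1 − m)²⁰ − 20m(1 − m)¹⁹. The number left is 37 × (1 − share).

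| Assumed m | Withdrawn, cumulative | Left of 37 per group | Withdrawn, consecutive |
|---|---|---|---|
| 1% | 1.7% | 36.4 | 0.2% |
| 2% | 6.0% | 34.8 | 0.7% |
| 5% | 26.4% | 27.2 | 4.5% |
| 10% | 60.8% | 14.5 | 16.1% |

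On the cumulative reading, m of about 2.7% would use up the whole 10% allowance.

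**Illustration of bias.** Suppose there is no true effect, shares wE and wC are withdrawn in the expressive and control arms, and withdrawn interns are D standard deviations more stressed than those who remain, equally in both arms. The group difference among those who remain is −(wE − wC) × D. All three inputs are assumptions.

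| wE, wC | D = 0.25 | D = 0.5 | D = 1 |
|---|---|---|---|
| 10%, 10% | 0 | 0 | 0 |
| 20%, 10% | −0.025 SD | −0.05 SD | −0.10 SD |
| 30%, 10% | −0.05 SD | −0.10 SD | −0.20 SD |

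The last row is 0.05/0.69 = 7% to 0.20/0.69 = 29% of the planned effect. If the control arm lost more, or the withdrawn were less stressed, the sign would reverse.

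**The case against.** The strongest reply is that no contradiction is proved. The protocol never says that measurement stops. Section 11 states intention to treat without exception, Section 10 sets no adherence condition, and Section 8 sends one link to everybody. Section 5 could mean only that the writing ends. Handling of withdrawn participants and of missing data is also commonly left to an analysis plan, which is not shown. **What stands:** the concern is conditional, and the size of any harm is unknown. **What does not:** none of those sentences says that a withdrawn intern still counts as a participant. An analysis plan can define a population or impute values, but it cannot collect questionnaires that were not sent.

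A second reply is that the rule and timetable are the same in both arms and that Section 6 already allows 10% loss. Equal withdrawal and equal prognosis would indeed give zero bias in the illustration. But the allowance protects numbers, not comparability, and the different tasks give no assurance that misses will be equal.

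Third, under Section 7 a coin toss assigns hospitals to the arms and interns are then sampled within each hospital, so the groups are already confounded with hospital. That is true, and continued measurement does not cure it. It is no reason to add selection on adherence.

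Finally, the neighbouring criterion, termination of the internship, is equally silent about measurement. That is fair, but it raises separate questions and does not weaken this point.

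**Conclusion.** The concern holds, as a conditional. What rests on the document alone is that the rule can act only before the first post-baseline measurement, that the protocol does not provide for measurement afterwards, and that without it a withdrawn intern is absent from every model in Section 11. On the ordinary reading of withdrawal, the analysis called intention-to-treat would be restricted to interns who kept submitting.

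The loss per affected intern is complete, 20 of 20 post-baseline records. How many interns would be affected, and the size and direction of any bias, cannot be derived; the tables of withdrawal and bias above rest on assumed rates. This should be fixed, with medium confidence, because the protocol may have intended continued measurement without saying so.

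**What to change.** Reconcile Sections 5 and 11.

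- **Section 5:** state whether the two misses are cumulative or consecutive, and that reaching the limit is recorded as non-adherence and does not end outcome measurement. These interns continue to receive the existing Wenjuanxing link at all four post-intervention times unless they withdraw consent.
- **Section 11:** state that every allocated intern with any post-baseline data is analysed in the allocated group, regardless of the number of submissions.

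Whether an intern goes on writing after two misses, what happens when an internship ends, and any per-protocol analysis are outside this point.

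The cost is about three sentences and a few more online questionnaires through a link that already exists. Some of these interns will not respond, and those who answer none of the four questionnaires remain outside the model; the change does not solve that. Including interns who wrote less may also give a slightly smaller estimated effect if the writing works. That is a consequence of estimating the effect in everyone allocated, and says nothing about the direction of the bias discussed above.

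### Section 6 powers stress at the end of the 10-week programme, but the Section 11 model tests one effect averaged over that visit and three later ones, so the stated 80% power is not that of the planned test

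*Protocol*

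**What the plan says.** Four parts of the protocol bear on what the primary comparison is.

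- **Section 6 (Sample Size)** uses the formula for two independent means, with a two-sided alpha of 0.05. The assumed effect is a standardised difference of 0.69, and Section 6 ties both that effect and the primary label to one time: it is a difference "in clinical practice stress by Stress Rating Scale for Nursing Students in Practice after 10 weeks of intervention (primary outcome"). The resulting size is given as "we require 33 participants per group to attain a power of 80" per cent. Attrition raises the total: "Accounting for an expected 10% loss to follow-up, we should include 74 participants".
- **Sections 2 and 3 (Research Questions, Research Objectives)** put the stress question at four post-baseline visits. The first specific objective compares the two kinds of writing "in managing clinical practice stress among student nurse interns between intervention and control groups at immediate and 4-week, 8-week, and 12-week follow-up". No visit is ranked above another.
- **Section 10 (Outcome Measures)** names clinical practice stress as primary without a time. It schedules a baseline, a measurement the day after the programme ends, and participants are then "followed up at 4 weeks, 8 weeks, and 12 weeks after the end of the intervention".
- **Section 11 (Data Analysis)** specifies a GEE with an exchangeable working correlation and robust standard errors. "Data from all available time points will be used". The stated independent variables are treatment group and the baseline value of the outcome, with age and sex added in a further model for the primary endpoint. Neither visit nor a group-by-visit interaction is listed.

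**The concern.** Section 9 has the writing last ten weeks in both arms, so three of the four visits fall 4, 8 and 12 weeks after it has stopped. The difference when the programme ends and the difference averaged over that visit and the next 12 weeks are separate quantities. Section 6 powers the first. Section 11, as written, tests the second.

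The result therefore depends on how long the effect lasts, which the sample size does not consider. If the effect fades, averaging dilutes the difference for which the trial was sized, and a programme that works at ten weeks could miss significance. If the effect lasts, the average is the more powerful test. In neither case does the stated 80% describe it. A reader of the final report could also not tell from Sections 2, 3 and 10 which of the four visits was meant to carry the conclusion.

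**Working it through.** **Step 1: reproduce Section 6.** Inputs from Section 6: effect size 0.69, two-sided alpha 0.05 (the formula uses Z at 1−α/2), power 80%, loss 10%.

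- n per group = 2 × ((1.960 + 0.842) / 0.69)² = 32.97, rounded up to 33.
- Normal-approximation power at 33 per group = 80.0%.
- 33 / 0.90 = 36.7, rounded up to 37 per group, 74 in total.

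The plan's figures are correct for one unadjusted comparison at one visit.

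**Step 2: the quantity that Section 11 tests.** With complete data and no visit term, the group coefficient is the difference in the mean of the four visits. Further inputs are assumptions, because the protocol gives none: equal SD σ at each visit, and one correlation ρ (0.3, 0.5 or 0.7) between all visits including baseline. The figures use 33 evaluable per arm. Like the plan's own formula, they leave hospital-level allocation aside.

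- Variance of a four-visit mean: σ²(1 + 3ρ)/4.
- Its covariance with baseline is ρσ², so adjusting for baseline removes ρ²σ². The adjusted factor is v = (1 + 3ρ)/4 − ρ², which is 0.385, 0.375 and 0.285 for the three values of ρ.
- For a single visit the adjusted factor is 1 − ρ², which is 0.91, 0.75 and 0.51.
- Power = Φ(d / √(2v/33) − 1.96), with d in SD units.

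**Step 3: average effect if the difference is 0.69 at the end of the programme.**

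- Halving every 4 weeks: (0.69 + 0.345 + 0.1725 + 0.08625)/4 = 0.323.
- Linear fall to zero at week 12: (0.69 + 0.46 + 0.23 + 0)/4 = 0.345.
- Sustained: 0.69.

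Worked case, halving with ρ = 0.3: √(2 × 0.385/33) = 0.153; 0.323/0.153 − 1.96 = 0.16; Φ = 0.56.

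**Step 4: baseline-adjusted power, 33 per arm.**

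| Test and pattern | ρ = 0.3 | ρ = 0.5 | ρ = 0.7 |
|---|---|---|---|
| Four-visit average, effect halves every 4 weeks | 56% | 57% | 69% |
| Four-visit average, linear fall to zero | 62% | 63% | 75% |
| Four-visit average, effect sustained | >99% | >99% | >99% |
| End-of-programme visit alone, 0.69 SD | 84% | 90% | 98% |

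**Step 5: where the two tests break even.** The average has more power when its effect, as a share of the end-of-programme effect, exceeds the ratio of standard errors: √(0.385/0.91) = 0.65, √(0.375/0.75) = 0.71 and √(0.285/0.51) = 0.75. The two fading patterns give 0.323/0.69 = 0.47 and 0.345/0.69 = 0.50, below all three thresholds.

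**The case against.** The strongest defence is that Sections 2, 3 and 11 agree on using all four visits, so Section 6 is the outlier. A four-visit average is a legitimate primary quantity. It keeps a single test at 5%, and it beats the single-visit test if enough of the effect persists (Step 5). The fading patterns and correlations are assumptions. All of this stands. It bears on which remedy to choose and on the direction of the error; it does not remove the mismatch, because Section 6 still attaches both the primary label and the power to one visit.

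It may also be said that a SAP, not shown here, could add visit terms. But Section 11 is not silent: it lists the model's independent variables. A SAP that changed them would depart from the protocol.

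Three stronger readings are tempting, and the documents do not support them.

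- **Power collapses to 32–48% (halving) or 36–53% (linear fall).** Those ranges come from the unadjusted variance (1 + 3ρ)/4. Section 11 puts baseline in the model, so they are not the power of the planned test.
- **The type I error is inflated.** The pooled coefficient is one test, and averaging over visits leaves its alpha at 5%. Only if the four visits were tested one by one at 5%, with any one counting as success, would the chance of at least one false positive be about 13–17% (simulated, ρ = 0.7 to 0.3). Section 11 does not state such testing.
- **No primary time point is named.** Section 6 names one. The omission is in Sections 2, 3, 10 and 11.

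**Conclusion.** The point holds as an inconsistency between the powered and the analysed quantity. The arithmetic in Section 6 is right, but it belongs to a test that the Section 11 model does not perform.

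The consequence can go either way. Under the assumptions in Step 2, the planned test has 56–75% power across the two fading patterns and over 99% with a sustained effect, against 84–98% for a baseline-adjusted test at the end of the programme. It cannot be said that the trial is underpowered, because the documents give no pattern of persistence. What can be said is that the protocol does not consider persistence and that its 80% is not the power of its planned primary analysis. The correction should be made before outcome data are seen.

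**What to change.** Carry the Section 6 definition through the protocol.

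- **Sections 3 and 10:** state that the primary endpoint is the between-group difference in the Stress Rating Scale at the assessment on the day after the programme ends. Make the 4-, 8- and 12-week differences secondary, as measures of persistence.
- **Section 11:** add visit (categorical) and group-by-visit terms, and take the end-of-programme contrast as the primary test. Without this, Sections 3 and 10 would name an endpoint that the model cannot estimate.

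The cost is wording in three sections and the extra model terms, with no new participants or measurements. There are two downsides. A benefit that appears only at a later visit could be reported only as secondary, and if the effect persists the single-visit test has less power than the average.

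If the sponsor prefers the four-visit average as primary, that is coherent too. Section 6 must then say so and restate its power for that average, giving the assumed correlation and course of the effect over the visits.
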